2. SYNOPSIS

Study Title	Neuroimaging Approaches to Deconstructing Acupuncture for Chronic Pain
Study Sponsor	National Institutes of Health, National Center for Complementary and Alternative Medicine Grant Number: R01AT007550
Study Objective	To evaluate the impact of acupuncture-induced somatosensory afference on altered neurobiology and analgesia in FM.
Study Design	This study design has two components: 1) a cross sectional assessment of brain chemistry, connectivity and response to pain in healthy controls and age- and sex-matched fibromyalgia patients, and 2) a longitudinal assessment of the same fibromyalgia patients randomized to either electro-acupuncture (EA) or mock laser acupuncture (ML).
Study Interventions	Electro acupuncture and mock laser acupuncture. Treatments will be delivered at 2x/week for 4 weeks, for a total of 8 treatments.
Study Duration	The study duration for healthy controls will be 1 week, with a 4 week screening window. The study duration for fibromyalgia patients will be up to 10 weeks: 4- week screening window prior to baseline; 1-week of baseline, 4 week treatment period, and 1 week of follow up.
Sample Size and Population	We will evaluate 40 healthy controls and 80 fibromyalgia patients (n=40 EA and n=40 ML). Demographics will be representative of the population of southeastern Michigan.

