7. STUDY DESIGN

7.1. Overall Design

Our overall goal is to understand the role somatosensation plays in modulating analgesia and neuroimaging markers related to altered neural processing of pain in FM (Table 1; Figure 2). Eighty (80) FM women patients will be evaluated with MRI at baseline and after acupuncture treatment (electro-acupuncture, EA; mock laser acupuncture, ML; n=40 per group). Treatments will be delivered at 2x/week for 4 weeks, for a total of 8 treatments. An additional 40 healthy age-matched adult women will serve as a control for neuroimaging markers collected from baseline FM patients, and will allow us to assess central pain pathology in our population (Aim 1). The HCs will not be treated with acupuncture since the goal of this investigation is to investigate potential mechanisms for acupuncture in chronic pain patients. In addition to our neuroimaging outcomes, we will also assess clinical and experimental pain outcomes during the study period from all subjects. These data in combination with other outcomes will be used to perform secondary analyses.

Table 1 – Neuroimaging Outcomes

Outcome	fMRI Protocol	Rationale
Clinical Pain	- resting fcMRI and ¹ H-MRS	Neuroimaging markers for clinical pain directly reflect our primary clinical outcome. Markers are needed for localized brain neurochemistry and associated network connectivity and their relation to clinical pain.
Experimental Pain	- fMRI with pressure pain and conditioned pain modulation.	Protocols for brain response to experimental pain are more mature than for clinical pain (facilitating comparison to prior research) and allow the assessment of hyperalgesia and allodynia.

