8. PATIENT SELECTION AND ENROLLMENT

8.1. Patient Eligibility

8.1.1. Inclusion Criteria

Inclusion Criteria for Fibromyalgia Participants

- Must have self-reported FM symptoms for at least one year and also meet the newly proposed Wolfe et al 2011 criteria for FM. Continued presence of pain more than 50% of days.
- Pain greater than or equal to 4 on a 10cm Visual Analog Scale (VAS) for pain; 7-day recall; [Note: The VAS is widely used in clinical pain research and as such we chose to use it for inclusion criteria and for clinical pain assessment below. Within our group numerical ratings scales 0-100 are more commonly used in quantitative sensory assessment, and as such we chose to use NRS scales for evoked pain assessments below.]
- Willing to limit the introduction of any new medications or treatment modalities for control of FM symptoms during the study.
- Able to travel to the study site to receive acupuncture treatments up to two times weekly.
- Over 18 and under 65 years of age.
- Right-handed.
- Female.
- Capable of giving written informed consent.

Inclusion Criteria for Healthy Control Participants

- Over 18 and under 65 years of age.
- Female.
- Right-handed.
- Pain equals 0 on a 10cm Visual Analog Scale (VAS) for pain; 7-day recall
- Willing to complete all study procedures.
- Capable of giving written informed consent.

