11. STATISTICAL CONSIDERATIONS

11.1. Aim 1: At baseline, characterize altered somatosensory neurocircuitry underlying chronic pain in FM.

Hypothesis 1: Using resting fcMRI, the insula in FM patients will show more correlation with DMN, and more anti-correlation with SMN, compared to HC.

We will use dual-regression independent component analysis (ICA) to evaluate resting connectivity between DMN/SMN and insula. Two-sample t-tests will compare FM vs. HC, cluster-corrected at $p=0.05$.

Based on our previous studies, assuming DMN connectivity z score (middle insula region) of 1 for a fibromyalgia patient vs. 0.5 for a healthy control with a common standard deviation of 0.5, we will expect a typical relative effect of 1 (mean ICA-derived z score over its standard deviation). Similar effects (negative connectivity values) are expected for SMN-derived biomarkers. With the planned numbers of subjects we will have the power exceeding 97% to detect the effects by a two-sided t-test.

Hypothesis 2: Using $^1\text{H-MRS}$, FM patients will show pain related increased Glx and reduced levels of GABA within the insula and S2 as compared to HC.

Metabolite concentration from regions of interest will be assessed using spectra data input into LCModel. A two-sample T-test will compare FM vs. HC, significant at $p=0.05$.

Our sample size calculation for difference between FM and HC assumes (from pilot data) that Glx, a proxy for glutamate concentration, has mean(SD) = 10.5(1.4) in arbitrary institutional units (AIU) and a FM-HC relative difference in excess of 10%. Thus we conservatively hypothesize an average Glx around 11.5 AIU and GABA around 1.3 mmol/kg in the FM group. We conclude that we will have the power of at least 84% for the GABA and 81% for the Glx based on a two-sided t-test with unequal N (80 in FM vs. 20 in HC) at the significance level of 0.05.

Hypothesis 3: Using evoked pain fMRI, FM patients will be more sensitive to evoked pressure pain and demonstrate greater insula activation to pain stimuli, compared to HC.

A general linear model will assess brain response to experimental pain from a block design BOLD fMRI run. A group level FM - HC difference map will use a two sample t-test, cluster corrected at $p=0.05$.

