12.3.2 Shared Data

High quality structural and resting state functional images taken from the baseline and follow-up imaging sessions (visit 2 and 12) for fibromyalgia participants and from healthy control's sole baseline imaging session (visit 2). In addition to these image files, we will also submit relevant metadata (sex, age, diagnosis). A list of subject IDs and acquisition dates will be provided to UCLA each time data is transmitted.

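### Aim 1 matches patients and controls on age, but no analysis of the FM–HC contrast names age, so intervals may be too wide and any leftover age difference uncorrected

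*Combined protocol and SAP*

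**What the plan says.** **Design.** The synopsis describes a cross-sectional comparison of "healthy controls and age- and sex-matched fibromyalgia patients", and section 7.1 says "An additional 40 healthy age-matched adult women will serve as a control". All participants are women, so age is the only stated matching variable that can vary. Section 8.1.1 admits a wide range, "Over 18 and under 65 years of age", for both cohorts and contains no matching rule. No matching ratio, tolerance or procedure is given anywhere.

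**Data.** Demographics are collected at screening in both cohorts (sections 3.1 and 3.2). Section 12.3.2 lists age among the items to be shared: "relevant metadata (sex, age, diagnosis".

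**Analysis, section 11.1.**
- Hypothesis 1, resting connectivity: "Two-sample t-tests will compare FM vs. HC", with cluster correction.
- Hypothesis 2, Glx and GABA: "A two-sample T-test will compare FM vs. HC".
- Hypothesis 3, evoked-pain activation: "A group level FM - HC difference map will use a two sample t-test".

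None of these has a covariate. The group-level general linear model in section 9.3.3 names none either. The statistical row of the synopsis lists both t-tests and linear regression for the FM–HC biomarker comparison, without saying what enters the regression.

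**The concern.** Matching on age makes the two groups' mean ages alike. If age is related to the biomarker, the difference in means then varies less from study to study than two independent samples would allow. The ordinary t-test does not know this. It leaves the age-related variance in its error term, so it rejects too seldom under the null and reports an interval that is too wide. Where matching is imperfect, the t-test also has no means of removing the remaining age difference from the contrast.

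At stake are the width of the intervals for the Aim 1 contrasts, the actual error rate of the tests, and protection against leftover age differences. There is a smaller pre-specification issue as well: with t-tests in one place and an unspecified regression in another, the choice between an unadjusted and an adjusted result is open until the data are seen.

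**Working it through.** **Inputs from section 11.1.** Glx: reference mean 10.5, SD 1.4, FM mean about 11.5, so d = (11.5 − 10.5)/1.4 = 0.714. Connectivity (Hypothesis 1): 1 against 0.5 with SD 0.5, so d = 1. Two-sided tests; the 0.05 level is stated for the metabolites and assumed for Hypothesis 1. The planned groups are 80 FM and 40 HC (synopsis, section 7.1); the Glx power statement uses 80 and 20.

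**Step 1: reproduce the plan's figures.** Unadjusted t-test, noncentral t, noncentrality d·√(n₁n₂/(n₁+n₂)).
- Glx, 80 vs 20: 0.714 × √(1600/100) = 2.857, power 80.8% (stated 81%).
- Hypothesis 1, 80 vs 20: 1 × 4 = 4, power 97.7% (stated as exceeding 97%).
- GABA cannot be reproduced, because no SD or control mean is given.

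At the planned 80 vs 40, √(3200/120) = 5.164. Glx has noncentrality 3.689 and power 95.5%; Hypothesis 1 has power 99.9%.

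**Step 2: add age.** Let R² be the share of within-group biomarker variance explained by age. No document gives it, so the values below are assumptions. With balanced ages the residual SD becomes SD·√(1 − R²), the standardised effect d/√(1 − R²), and the degrees of freedom drop from 118 to 117.

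| R² (assumed) | Fall in SE, 1 − √(1 − R²) | Glx power, 80 vs 40 | Hypothesis 1 power, 80 vs 40 |
|---|---|---|---|
| 0 (unadjusted) | – | 95.5% | 99.9% |
| 1% | 0.5% | 95.7% | 99.9% |
| 4% | 2.0% | 96.2% | 99.9% |
| 10% | 5.1% | 97.1% | over 99.9% |
| 20% | 10.6% | 98.3% | over 99.9% |
| 30% | 16.3% | 99.2% | over 99.9% |

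In Glx units, the unadjusted standard error is 1.4 × √(1/80 + 1/40) = 0.271, a 95% half-width of about 0.54. At R² = 10% the half-width is about 0.51, and at 30% about 0.45.

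**Step 3: error rate under close matching.** If the mean ages are equal, the true variance of the difference is (1 − R²) times what the t-test assumes. The actual two-sided level is therefore about 2·P(Z > 1.96/√(1 − R²)).
- Correlation 0.3 (R² = 9%): 1.96/0.954 = 2.055, level about 4.0%.
- Correlation 0.5 (R² = 25%): 1.96/0.866 = 2.263, level about 2.4%.

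A simulation of 4,000 trials, with each control's age matched to two patients, agrees within simulation error. The t-test rejected in 4.3% and 1.9% of null trials, against 5.2% and 4.8% with age in the model. In the same simulation Glx power rose only from 96.8% to 97.5% at correlation 0.3, and from 97.5% to 98.7% at 0.5. Close matching already gives the unadjusted comparison part of the benefit, so the table's 95.5% starting point slightly overstates the power to be gained.

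**Step 4: leftover imbalance.** The shift in the contrast, in SD units, is the correlation times the age difference in SDs. With an assumed correlation of 0.3, an age difference of 0.25 SD gives 0.3 × 0.25 = 0.075 SD, about 10% of the Glx effect (0.075/0.714). A difference of 0.4 SD gives 0.12 SD, about 17%. A linear age term removes the linear part of this shift.

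**Limit.** These calculations are for a single regional measure, such as a metabolite level in one voxel. They do not carry over to the cluster-corrected maps of Hypotheses 1 and 3.

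**The case against.** The strongest reply is that little is lost. The plan already contemplates regression for this comparison, planned power is high, and the benefit depends on an association that the documents never mention. At a correlation of 0.2 or less the gain is negligible. All of that stands, and it limits the point to a modest improvement.

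Four stronger readings are tempting and are not supported:
- *A reader might infer that the plan has no regression for Aim 1.* The synopsis lists it. What is missing is any named covariate, and agreement between the synopsis and section 11.1.
- *A reader might infer that substantial power is being thrown away.* From an effect with just 80% power at 80 vs 40 (d about 0.547), R² of 5% to 30% would raise power to between 82% and 92%. That effect appears nowhere in the plan; its own effects start at 95.5% and 99.9%.
- *A reader might take the 80 to 40 split as a sign of age imbalance.* Unequal group sizes say nothing about age. Imbalance is possible because no matching procedure is described, but nothing shows that it will occur.
- *A reader might infer that omitting age undermines the stated power or produces false positives.* The Glx and Hypothesis 1 figures reproduce without it, and with close matching the t-test errs on the conservative side.

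**Conclusion.** The point holds as a low-cost improvement. The design matches on age, age is recorded, and no analysis uses it. If age is related to a biomarker, the planned t-test is conservative under close matching, with an interval too wide by an amount that depends on R²: under 1% of the standard error at R² = 1%, about 5% at 10%, about 16% at 30%. The value lies in interval width, a correct error rate and correction of leftover imbalance; the power gain for the plan's own effects is small to nil.

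This rests on an assumed age–biomarker association, a roughly linear age effect that is similar in the two groups, and single regional outcomes. Separately, the Glx power statement uses 20 controls where 40 are planned; that moves Glx power from about 81% to 95.5%, far more than age adjustment does.

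**What to change.** In section 11.1, make the main analysis for Aim 1 Hypotheses 1 to 3 a linear model of the biomarker on group and age, reporting the group coefficient with its 95% confidence interval. For the connectivity and evoked-pain maps, enter age as a covariate in the group-level general linear model. Keep the unadjusted two-sample t-test as a sensitivity analysis. Change the synopsis to name the same model and covariate, so that the two places agree.

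The cost is one degree of freedom (117 instead of 118 with 80 and 40 participants). No new data, visits or participants are needed.

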Changes in connectivity z-score for a typical connectivity biomarker are expected to follow a different slope in FM vs. HC patients in response to pressure pain. Based on our previous studies we expect the slope of 1.3 vs. 0.8 (FM vs. HC, respectively) with the standard deviation of the pain score of approximately 1 and standard deviation of the connectivity score at a given level of pressure pain of around 0.5. This ensures we will have over 86% power to detect a difference in connectivity responses to evoked pain.

ROC Analysis

In order to characterize the potential of biomarkers to predict the disease, a decision rule predicting FM status, a binary outcome, based on connectivity, Glx/GABA and evoked pain biomarkers. Our primary method for rule development will be logistic regression. Stepwise variable selection procedures using Likelihood Ratio tests and Akaike Information Criterion (AIC) will be performed to identify the set of significant predictors. A cutpoint on the linear predictor in the logistic model will define the decision rule with values above the cutpoint for a particular subject interpreted as prediction of treatment success for the subject. A set of rules obtained by varying the cutpoint will be summarized by the Receiver-Operating-Characteristic (ROC) curve plotting sensitivity by 1-specificity of the rule. The area under the ROC for the model will characterize the quality of prediction. The area under the ROC will serve as the overall measure of discriminative ability of the model. In order to obtain a realistic estimate of ROC, cross-validation will be used when estimating sensitivity and specificity corresponding to various cutoff values.

The assessment of power is based on a test for area under the ROC. We hypothesize that an area of 0.7 can be achieved. A test for area <0.6 vs. >0.6 shows that we will have 83% power to discriminate area of 0.7 from 0.6 or less with 80 FM patients and 20 controls, using a two-sided test at the significance level of 0.05. This indicates that we will have the precision of at least 0.1 on the area under ROC scale.

11.2. Aim 2: Evaluate longitudinal desensitization effects of electro- and mock laser acupuncture interventions on the neurocircuitry underlying chronic pain in FM, correlate the change in pain with changes in neurocircuitry physiology, study neuroimaging biomarkers as mediators for the treatment effect.

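### The Aim 1 Hypothesis 2 and ROC powers are computed with 20 healthy controls although the design plans 40; this understates the Glx and GABA powers, and the ROC power needs its own recalculation

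*Combined protocol and SAP*

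**What the plan says.** The design text gives the control count twice. The synopsis (Section 2) says "We will evaluate 40 healthy controls and 80 fibromyalgia patients (n=40 EA and n=40 ML"). Section 7.1 says "An additional 40 healthy age-matched adult women will serve as a control for neuroimaging markers collected from baseline FM patients", alongside "Eighty (80) FM women patients will be evaluated with MRI at baseline and after acupuncture treatment".

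Section 11.1 uses a different count, also twice. Under Hypothesis 2, the power of 81% for Glx and at least 84% for GABA comes from a "two-sided t-test with unequal N (80 in FM vs. 20 in HC"), at a two-sided level of 0.05. Under ROC Analysis, the power of 83% to separate an area of 0.7 from 0.6 is stated "with 80 FM patients and 20 controls, using a two-sided test at the significance level of 0.05".

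The other two Aim 1 hypotheses name no control count. Hypothesis 1 claims power above 97% at the planned numbers. Hypothesis 3 claims over 86% and gives no group sizes.

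**The concern.** A power statement should describe the trial that will be run. Here the printed powers for Hypothesis 2 and the ROC analysis belong to a study with half the planned controls. The documents do not present 20 as an evaluable number after losses, a spectroscopy subset or an interim count. The only other 20 in Section 11 is the interim count of 20 patients per treatment arm (Sections 11.2 and 11.3), and those are FM patients.

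Two things are at stake. The first is how a null FM-versus-control result would be read: the standardised difference detectable with 80% power is about 0.71 at 80 vs 20 and about 0.55 at 80 vs 40. The second is whether the stated rationale supports 40 controls at all, since no explicit calculation in Section 11.1 uses that number.

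**Working it through.** **Inputs.** From Section 11.1, Hypothesis 2: Glx mean 10.5 and SD 1.4, read here as the control mean and common SD; FM mean 11.5; two-sided alpha 0.05. From Sections 2 and 7.1: 80 FM, 40 controls. From Section 11.1: 80 FM, 20 controls. From ROC Analysis: area 0.7 against 0.6.

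**Glx.** Standardised difference d = (11.5 − 10.5)/1.4 = 0.714. Power comes from the noncentral t with df = n₁ + n₂ − 2 and noncentrality d/√(1/n₁ + 1/n₂).

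- 80 vs 20: √(1/80 + 1/20) = 0.250, noncentrality 2.857, df 98, critical value 1.984. Power is **80.8%**, which reproduces the stated 81%.
- 80 vs 40: √(1/80 + 1/40) = 0.1936, noncentrality 3.689, df 118, critical value 1.980. Power is **95.5%**.

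So 81% is a 20-control figure. A one-sided test at 80 vs 20 gives 88.3% and does not match. Taking the difference as exactly 10% of 10.5 (1.05) gives 84.4% at 80 vs 20 and 97.0% at 80 vs 40, so the gap between the two designs remains.

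**GABA.** Only the FM value (1.3 mmol/kg) is given. Solving for the d that yields 84% at 80 vs 20 gives d = 0.746. The same d at 80 vs 40 has noncentrality 0.746/0.1936 = 3.85 and power **96.9%**. This takes the stated 84% as correct.

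**Hypothesis 1.** d = (1 − 0.5)/0.5 = 1. Power is 97.7% at 80 vs 20 and 99.9% at 80 vs 40. The claim of more than 97% is true at either size.

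**ROC.** No method is stated. I assume Hanley-McNeil variances: Var(A) = [A(1 − A) + (n₁ − 1)(Q₁ − A²) + (n₂ − 1)(Q₂ − A²)]/(n₁n₂), with Q₁ = A/(2 − A) and Q₂ = 2A²/(1 + A). The result depends on which group is taken as n₁, and on whether the critical value uses the null SE, Φ[(0.1 − 1.96·SE₀.₆)/SE₀.₇], or the alternative SE throughout, Φ[0.1/SE₀.₇ − 1.96]. All four versions:

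| n₁, n₂ | SE at 0.6 | SE at 0.7 | Power, null SE | Power, alternative SE |
|---|---|---|---|---|
| 80, 20 | 0.0679 | 0.0596 | 29.0% | 38.9% |
| 20, 80 | 0.0735 | 0.0705 | 26.6% | 29.4% |
| 80, 40 | 0.0535 | 0.0481 | 45.9% | 54.7% |
| 40, 80 | 0.0560 | 0.0528 | 42.7% | 47.3% |

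The range is therefore about 27–39% with 20 controls and 43–55% with 40. The stated 83% is not obtained in any cell. With a null of 0.5 instead, n₁ = 80 and n₂ = 20, the null SE is 0.0725 and the power is Φ[(0.2 − 1.96 × 0.0725)/0.0596] = Φ(0.97) = 83.4%, which matches the printed figure.

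**The case against.** The strongest reply is that the mismatch does no harm. With 40 controls the Glx and GABA powers exceed the printed ones, the GABA statement is worded as a lower bound and stays true on the plan's own assumption, and no test, visit or randomised comparison changes. The Glx inputs are all printed, so a reader can recompute that power at either size. Two design statements agree on 40, so the power text is the likelier error. All of this stands, and it keeps the point at the level of a correction to stated figures.

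Four stronger readings are tempting, and the documents do not support them.

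- *All Aim 1 powers use 20 controls.* Only Hypothesis 2 and the ROC analysis say so. Hypothesis 1 is compatible with either count, and Hypothesis 3 states none.
- *Aim 1 is underpowered because of the mismatch.* For Glx and, conditionally, GABA the error runs the other way.
- *Every listed power is understated, so the ROC figure would also rise above 83%.* Under the variances assumed here it is overstated at both sizes, and the control count is not its main problem.
- *Only 20 controls will be enrolled.* Nothing in the design text says this.

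**Conclusion.** The inconsistency is real and not a one-off slip: 40 controls in two design statements, 20 in two power statements, with no explanation. For Glx the printed 81% should read about 95.5% if 40 controls are enrolled, roughly 15 points higher. This takes 10.5 as the control mean and 1.4 as the common SD. For GABA the change is from 84% to about 97%, roughly 13 points, and is only as sound as the unverified 84%. Both errors are conservative.

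The ROC power is wrong in the other direction. Against the stated null of 0.6 it is about 43–55% at 80 vs 40, not 83%. This rests on Hanley-McNeil variances and a normal approximation. That 83% was computed against a null of 0.5 is an inference from one matching calculation; the plan does not say so.

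**What to change.** 1. Confirm the number of healthy controls. If it is 40, restate the Hypothesis 2 powers at 80 vs 40 (Glx about 95.5%; GABA about 97% if its inputs bear this out) and print the GABA control mean and SD used.
2. Recompute the ROC power at 80 vs 40 against the stated null of 0.6, name the variance method, and print the lower figure. If another null was used, state it and change the description of the test to match.
3. State the group sizes behind the Hypothesis 1 and Hypothesis 3 powers.
4. If only 20 controls are intended, leave the Glx and GABA powers as they are, correct Sections 2 and 7.1, supply the GABA inputs, and still revise the ROC statement.

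If 40 is confirmed, the cost is wording in Section 11.1 and a short recalculation, with no change to enrolment, visits or analyses. The one substantive consequence is that the plan would have to acknowledge a ROC power well below 83% against a null of 0.6.

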Hypothesis 2 : EA will more readily reduce Glx and increase GABA in the insula as compared to ML, which will not reduce Glx and GABA. The change in pain will correlate with change in insula GABA and Glx for EA but not ML. Glx and GABA will represent mediators for the treatment effect on change in pain.

Similar to above, linear mixed models and paired t-test analyses will evaluate, separately, Glx and GABA concentration levels taken from baseline and post-therapy H-¹MRS scans.

A reduction in the Glx of about 1.5 arbitrary institutional units (AIU) with a standard deviation not exceeding 0.6 is expected in the EA group. At the same time in the ML group a much smaller effect is expected (around 1 AIU, same standard deviation). This ensures 95% power when using a two –sided test. A similar analysis for differences in the change in GABA of 0.3 vs. 0.1 mmol/kg with a standard deviation of 0.25 gives 94% power to detect a difference.

Correlation between Glx/GABA and clinical pain (BPI) will be analyzed similar to the fcMRI biomarkers. The study has 94% power to detect correlations of 0.5 and higher.

Similar to fcMRI biomarkers, if Glx or GABA show less than 20% post-hoc power after half of the patients have been measured (correlation less than 0.18), their longitudinal measurements will be discontinued for the remaining patients.

Mediation Analysis is similar to the one proposed for connectivity.

Hypothesis 3: EA will more readily reduce pain-evoked fMRI activation in the insula as compared to ML, which will not reduce pain-evoked fMRI activation. The change in pain will correlate with change in insula response to evoked pain for EA but not ML. Insula response to evoked pain will represent a mediator for the treatment effect on change in pain.

Parameter estimates from evoked pain block-design fMRI scans will be used in a linear mixed model and post-hoc paired t-tests, similar to the approach described above.

Changes in connectivity z-score for a typical connectivity biomarker are expected to follow a different slope in EA vs. ML patients in response to pressure pain. Assuming the slope of 1.3 vs. 0.5 with the standard deviation of the pain score of approximately 1 and standard deviation of the connectivity z score at a given level of pressure pain of around 1. This ensures we will have over 94% power to detect a difference in connectivity by pressure pain slope responses with 40 patients per treatment group.

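### The powers stated under Hypothesis 3 of Aims 1 and 2 are for a connectivity-slope comparison, not for the planned tests of pain-evoked insula activation

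*Combined protocol and SAP*

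**What the plan says.** **Aim 1, Hypothesis 3 (section 11.1).** The hypothesis is that "FM patients will be more sensitive to evoked pressure pain and demonstrate greater insula activation to pain stimuli", compared with healthy controls. The test is a two-sample t-test on the FM minus HC difference map from the block-design run, cluster corrected at 0.05. Section 9.3.3 says that the group analysis takes single-subject contrast maps of equal pressure and equal pain against touch.

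The power paragraph that follows turns to connectivity. It says "we expect the slope of 1.3 vs. 0.8 (FM vs. HC, respectively"), with a "standard deviation of the pain score of approximately 1" and a "standard deviation of the connectivity score at a given level of pressure pain of around 0.5". It concludes that "we will have over 86% power to detect a difference in connectivity responses to evoked pain". It states no sample size, alpha or sidedness.

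**Aim 2, Hypothesis 3 (section 11.2).** The hypothesis is that EA reduces pain-evoked insula activation more than ML. The analysis reads "Parameter estimates from evoked pain block-design fMRI scans will be used in a linear mixed model", with post-hoc paired t-tests. The power paragraph again uses connectivity: slopes of 1.3 vs 0.5, pain SD 1, z-score SD 1, and "over 94% power to detect a difference in connectivity by pressure pain slope responses" with 40 patients per group.

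**The concern.** The quantity that is powered is not the quantity that will be tested. It differs in outcome (connectivity, not activation) and in estimand (a difference in slopes on pressure, not a difference in mean activation or in its change). Hypothesis 3 is one of three hypotheses in each of the two aims. If the activation result is null, a reader will set it against 86% or 94% power, and the plan has not shown that the activation tests have that power.

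A smaller matter is that the Aim 1 figure cannot be traced. Its paragraph gives no N, and the slopes and SDs it lists do not return 86% at either control-group size found in the documents.

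**Working it through.** **1. What is tested and what is powered**

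| | Planned test | Quantity in the power text |
|---|---|---|
| Aim 1 H3 | Cluster-corrected two-sample t-test on contrast maps of pressure or pain vs touch (9.3.3, 11.1) | FM vs HC difference in slope of connectivity z-score on pressure pain |
| Aim 2 H3 | Linear mixed model on block-design activation estimates, EA vs ML, baseline and post-therapy (11.2) | EA vs ML difference in slope of connectivity z-score on pressure pain |

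The nearest planned analysis to the powered one is connectivity during the 6-minute sustained cuff scan, which section 9.3.1 says will be handled like the resting scan. No regression of connectivity on pressure, and no comparison of such slopes between groups, is described. Neither the activation mean difference nor its SD appears in the documents, so the stated figures cannot be converted into power for the activation tests.

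**2. Reproducing the stated figures as slope tests**

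The standard error of a difference of two slopes is (residual SD / SD of predictor) × √(1/n1 + 1/n2). Power is taken from the noncentral t with n1 + n2 − 4 degrees of freedom, two-sided 0.05.

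*Aim 2.* Difference 1.3 − 0.5 = 0.8, both SDs 1, 40 vs 40. SE = √(1/40 + 1/40) = 0.2236; ratio 0.8/0.2236 = 3.58; power 94.2%. The stated 94% reproduces.

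*Aim 1.* Difference 1.3 − 0.8 = 0.5, predictor SD 1, residual SD 0.5. The paragraph gives no N. Hypothesis 2 in the same section uses a "two-sided t-test with unequal N (80 in FM vs. 20 in HC) at the significance level of 0.05", and the ROC paragraph also has 80 and 20. The Synopsis and section 7.1 plan 80 FM and 40 HC.

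- 80 vs 20: SE = 0.5 × √(1/80 + 1/20) = 0.125; ratio 4.0; power 97.7%.
- 80 vs 40: SE = 0.5 × √(1/80 + 1/40) = 0.0968; ratio 5.16; power 99.9%.

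Neither is 86%. To reach 86% at 80 vs 20, the residual SD would have to be about 0.65 or the slope difference about 0.38. At 80 vs 40 it would take about 0.84 or about 0.30.

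Several undocumented settings give 86–87%: 20 vs 20 (86.8%), 80 vs 11 (86.8%), 40 vs 13 (86.7%), 30 vs 15 (87.0%), or 80 vs 20 at two-sided alpha 0.005 (86.7%). The source cannot be identified.

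The formula treats the pain scores as fixed. Simulating them as normal lowers the results slightly, to 94.7% (80 vs 20), 99.8% (80 vs 40) and 92.1% (Aim 2). This does not bring Aim 1 to 86% at either documented control number.

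**3. What can be said about the activation tests**

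Without activation SDs, only a detectable standardised difference d can be given. For a single region, two-sided 0.05, 80% power and complete data, the normal approximation is d = (1.96 + 0.84) × √(1/n1 + 1/n2).

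- Aim 1, 80 vs 40: 2.80 × 0.1936 = 0.54; about 0.55 with the t distribution.
- Aim 2, change, 40 vs 40: 2.80 × 0.2236 = 0.63; 0.63 with the t distribution. Here d is in units of the SD of the within-patient change.

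These make no allowance for cluster correction. As an illustration only, an assumed effective alpha of 0.001 raises them to about 0.80 and 0.92 (normal approximation).

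**The case against.** Four points can be made for the plan.

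- **The Aim 1 sentence is literally true.** It says over 86%, and its inputs give 97.7% or 99.9%. This stands. A reader might infer from the failure to reproduce that the power is overstated; the documents do not support that, because the discrepancy runs in the safe direction. Nor do they support the inference that 20 per group was used, since other undocumented settings give the same figure.
- **The 94% is arithmetically correct.** This also stands. Only its relevance to the activation test is in question.
- **Connectivity during evoked pain is part of the study.** True for the sustained cuff scan. That supports planning a connectivity analysis, but it does not make a slope-on-pressure comparison the test of Hypothesis 3.
- **The Aim 2 paragraph may already concern pre-post change.** It opens by speaking of changes in the connectivity z-score, which in a longitudinal aim could mean within-patient change. The text is ambiguous, so one cannot say that it ignores the pre-post design. It is still about connectivity.

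None of this turns either figure into a power for an activation test.

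**Conclusion.** The mismatch holds for both aims. The stated 86% and 94% belong to a connectivity-slope comparison that the plan does not describe, and power for the planned activation tests is not stated and cannot be derived from the documents. This rests on the text alone.

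The arithmetic point is secondary and limited to Aim 1. Assuming two-sided 0.05 and either documented control number, 86% is a conservative bound that does not reproduce, and its origin is unknown. The Aim 2 figure is sound for the test it describes.

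A reader might conclude that the trial is underpowered for Hypothesis 3. The documents do not show that either; they leave the power unknown. The values 0.55 and 0.63 indicate scale for a single uncorrected region with complete data. They are not the detectable effects of the cluster-corrected map test, which needs larger ones.

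**What to change.** In sections 11.1 and 11.2, remove the 86% and 94% as power claims for Hypothesis 3. Alternatively, relabel them as applying to a connectivity-by-pressure slope analysis, describe that analysis, and give N and alpha for the Aim 1 figure.

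Then state power for the activation tests from the sponsor's own activation data: the between-subject SD for Aim 1 and the SD of within-patient change for Aim 2. Give N (40 controls, as in the design, not 20), alpha and sidedness.

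If no SDs are available, give detectable standardised differences at 80% power of about 0.55 (80 vs 40) and 0.63 (40 vs 40, change). Label them as single-region, two-sided 0.05, without cluster correction or dropout, and note that the cluster-corrected test needs larger effects.

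The cost is SAP wording and, where pilot activation data exist, a short calculation. Sample size, procedures and planned analyses stay as they are.
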